### 1.2.3 Toxicity data

The data described below reflect exposure to ibrutinib in a clinical trial that included 111 patients with previously treated MCL treated with 560 mg daily with a median treatment duration of 8.3 months. The following risks are discussed in more detail in the full prescribing information:

- Hemorrhage (5%)
- Infections (25%)
- Myelosuppression (41%)
- Renal Toxicity (67%)
- Second Primary Malignancies (5%)

Because clinical trials are conducted under widely variable conditions, adverse event rates observed in clinical trials of a drug cannot be directly compared with rates of clinical trials of another drug and may not reflect the rates observed in practice.

The most commonly occurring adverse reactions ( $\geq 20\%$ ) were thrombocytopenia, diarrhea, neutropenia, anemia, fatigue, musculoskeletal pain, peripheral edema, upper respiratory tract infection, nausea, bruising, dyspnea, constipation, rash, abdominal pain, vomiting and decreased appetite. The most common Grade 3 or 4 non-hematological adverse reactions ( $\geq 5\%$ ) were pneumonia, abdominal pain, atrial fibrillation, diarrhea, fatigue, and skin infections.

An evaluation of the safety data across 5 clinical studies (sponsored by Pharmacyclics & Janssen Scientific Affairs) including 392 subjects found moderate toxicities associated with ibrutinib treatment. The most common ( $> 10\%$ ) treatment-emergent adverse events (AEs) were diarrhea

Study Numbers: NU 14H06  
PCI-32765MCL2003Initial version: September 24, 2014  
AMD 11: ver. date 08.06.2022

(40.4%), fatigue (32.1%), nausea (24.0%), cough (17.6%), and peripheral edema (16.7%). These AEs are classified as grade 1 or 2 in severity and were not dose-limiting. Grade 3 or 4 adverse events were noted in about 45.8% of the patients, which were typically hematologic in nature (anemia 5.8%, thrombocytopenia 5.1%, and neutropenia 4.5%). Serious adverse events (SAEs) were experienced by 35.9% of subjects, which included pneumonia (4.5%), febrile neutropenia (3.2%), and atrial fibrillation (2.9%).

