#### **4.6 Duration of Therapy**

Patients may continue on ibrutinib maintenance therapy up to 4 years in the absence of disease progression or development of unacceptable toxicity; or patient preference (withdrawal of consent). Clinical suspicion of progressive disease (PD) or loss of response should be investigated radiographically, and will result in removal of active therapy if confirmed by clinical investigation.

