### 6.2 Secondary Endpoints

#### 6.2.1 Toxicity

All patients who receive at least one dose of ibrutinib will be evaluable for toxicity (including those who are replaced for efficacy endpoints). The study will use the CTCAE version 4.03 (see appendices for link) for reporting of adverse events. The occurrence and severity of each will be recorded.

After the study has been opened for 18 months, patients will be evaluated for an interim safety analysis. The PI along with the Northwestern Lymphoproliferative Disorders disease team and Quality Assurance will assess data to ensure there are no unexpected safety signals that have been observed at this time. See section 10.3.4 for details on the safety analysis.

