## 7.0 ADVERSE EVENTS

This study will be conducted in compliance with the Data Safety Monitoring Plan (DSMP) of the Robert H. Lurie Comprehensive Cancer Center of Northwestern University (please refer to the protocol page in NOTIS for additional information). The level of risk attributed to this study requires High Intensity Monitoring, as outlined in the DSMP. In addition, the study will abide by all safety reporting regulations, as set forth in the Code of Federal Regulations and as required by the NCI AdEERS Reporting Guidelines.

This study has been designated as an interventional study. As such, all adverse events and special situations, including pregnancies and product quality complaints, will be reported from the time a subject has signed and dated an Informed Consent Form (ICF) until 30 days after the last documented use of the product under the study within the study. Adverse events that result in treatment discontinuation will be followed until resolution or until the patient starts subsequent therapy, whichever comes first.

For the purposes of this study, the Janssen medicinal product is: Ibrutinib (Imbruvica)

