#### **10.3.2 Secondary Objectives**

To assess toxicity, all adverse events will be summarized as to type, severity, frequency, timing and attribution. Descriptive frequencies and proportions will be used for this analysis.

To determine rates of conversion from PR to CR, only patients who had a PR at the time of registration and who complete  $\geq 1$  complete cycle of ibrutinib maintenance therapy will be evaluable for this endpoint. These rates will be calculated as a proportion together with exact 90% confidence limits.

To determine median overall survival (OS) after 4 years, Kaplan-Meier curves will be determined for overall survival and the five-year point on this curve, along with 90% confidence limits, will be determined. Patients will be evaluated monthly for the first 6 months on treatment, then every 3 months thereafter. Patients who go off treatment will continue to be followed for survival up to a maximum of 4 years post-first dose. Follow-up will occur every 3 months (up to 2 years after the first dose of treatment) and then every 6 months thereafter (up to 4 years post-first dose).

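### Section 10.3.2 promises a summary of adverse event timing but names no method that accounts for time on drug, which can run from one dose to 4 years

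*Combined protocol and SAP*

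**What the plan says.** Toxicity is the first secondary objective (2.2.1). Section 10.3.2 states that "all adverse events will be summarized as to type, severity, frequency, timing and attribution", and then names the method: "Descriptive frequencies and proportions will be used for this analysis". On who is counted, 6.2.1 says: "All patients who receive at least one dose of ibrutinib will be evaluable for toxicity". This includes patients who are replaced for efficacy. On how long patients can be exposed, 4.6 says: "Patients may continue on ibrutinib maintenance therapy up to 4 years in the absence of disease progression". Section 7.0 sets the general reporting window from consent "until 30 days after the last documented use of the product under the study", so observation for most events follows time on drug. Section 7.2.5 makes an exception for other malignancies, which are reported through follow-up, including after progression.

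No section specifies, for adverse events, a rate per patient-year, a time-to-first-event or cumulative incidence method, or a summary of time on drug.

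**The concern.** The plan asks about timing but gives a tool that cannot answer the question. A count of events by period, divided by all treated patients, falls in later periods for two reasons: the risk may fall, or fewer patients may be left on drug and under observation. Without the number at risk or the time at risk, the two cannot be told apart.

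This matters because of what the trial adds. Sections 1.1 and 1.3 present ibrutinib maintenance after response as unexplored, and treatment may run for 4 years in patients who are already in remission. A positive result would support further testing, particularly in a randomised setting (10.2). Those planning that study would want to know how often harm occurs per year on drug and whether it continues. The plan uses Kaplan-Meier curves for PFS and OS, but names no time-based method for harm over the same period.

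**Working it through.** **Plan's own figure.** The toxicity analysis has none. The only design figure is N = 36 with success at 26 or more. Under the exact binomial it reproduces, with type I error 9.0% at 60% and power 91.1% at 80%. Nothing below changes it.

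**Inputs from the documents.** Maximum treatment is 4 years (4.6). Three-year PFS is 60% under the null and 80% under the alternative (10.2). There are 36 evaluable patients (10.2).

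**Assumptions, not in the documents.** The first-event hazard is constant at h = 0.10 per year. Stopping for reasons other than progression or death occurs at w = 0.05 to 0.15 per year. The 30-day tail after last dose is ignored; it adds at most 36 × 30/365 ≈ 3 patient-years.

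**Step 1: stopping hazard.** s = −ln(PFS at 3 years)/3 + w. The first term is 0.074 at 80% and 0.170 at 60%, so s runs from 0.124 to 0.320 per year.

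**Step 2: first events by year, over all treated patients.** For year k, the proportion is h/(h+s) × [exp(−(k−1)(h+s)) − exp(−k(h+s))].

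| | s = 0.124 | s = 0.320 |
|---|---|---|
| h/(h+s) | 0.446 | 0.238 |
| Year 1 | 0.446 × (1 − 0.799) = 9.0% | 0.238 × (1 − 0.657) = 8.2% |
| Year 4 | 0.446 × (0.510 − 0.408) = 4.6% | 0.238 × (0.283 − 0.186) = 2.3% |
| All 4 years | 26.4% | 19.4% |

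The hazard is the same in every year by construction, yet the year-4 proportion is about half (4.6/9.0) to about a quarter (2.3/8.2) of the year-1 proportion. That fall comes from stopping and from earlier first events, not from lower risk. The same events divided by time at risk give 10 per 100 patient-years in each year.

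**Step 3: what a rate would look like at this size.** Suppose mean time on drug is 2.8 years, within the 2.3 to 3.2 years that these assumptions give. Solving (1 − exp(−4s))/s = 2.8 gives s ≈ 0.190. Time at risk to first event is then (1 − exp(−4 × 0.290))/0.290 ≈ 2.37 years per patient, and 36 × 2.37 ≈ 85 patient-years. Nine first events give 9/85 = 10.6 per 100. The exact 90% Poisson limits for 9 are 4.70 and 15.71 events, or 5.5 to 18.5 per 100. Dividing first events by total time on drug (36 × 2.8 ≈ 101) would give 8.9 per 100, which is too low because it counts time after the first event.

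**Step 4: how finely time can be split.** With two periods, about 31 patient-years fall in the first 12 months and 54 later, and about 36 × exp(−0.290) ≈ 27 patients remain at risk at 12 months. If the 9 events split 3 and 6, the rates are 9.6 (2.6 to 24.9) and 11.1 (4.8 to 22.0) per 100. Four periods would leave about 2 events each. The exact 90% limits for 2 events are 0.36 to 6.30, an 18-fold range, which is too sparse to be useful.

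**The case against.** The strongest case on the other side is that the crude proportion is a legitimate target. Once every patient has reached 4 years or stopped, it estimates the chance that a patient starting this maintenance has the event on drug. Toxicity is descriptive here, the go/no-go rule rests on PFS, and safety action rests on the separate SAE boundaries in 10.3.4. The rate could also be added at reporting.

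All of this stands, and it limits the point to interpretation. It does not remove the gap, because timing is already promised and frequencies alone cannot show it. Naming the events and the window in advance also settles those choices before the results are seen.

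Three stronger readings might be inferred, and the documents do not support them.

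- **That only crude proportions are planned.** Timing is listed; what is missing is how it will be summarised.
- **That the crude proportion is a biased estimate of a true 4-year risk.** At h = 0.10, the risk if nobody stopped is 1 − exp(−0.4) = 33%, against a crude 19% to 26%. These answer different questions, so the gap is not an error. For early-onset events it would also be smaller.
- **That the results would look falsely toxic beside the background trial,** which treated 111 patients "with a median treatment duration of 8.3 months". No section plans that comparison. Those patients had a median of 3 prior treatments (1.2.2), while this trial enrols responders to first-line induction. Section 1.2.3 gives percentages without patient-years and itself cautions about comparing rates between trials, although its wording concerns another drug.

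**Conclusion.** The point holds as a gap between a stated aim and the named method. With exposure from one dose to 4 years, frequencies and proportions over all treated patients cannot give a rate per year on maintenance or show whether harm continues. Under the assumptions above, attrition and earlier first events alone would reduce the yearly proportion with a first event from 8–9% in year 1 to 2–5% in year 4. The size rests wholly on the assumed constant hazard and stopping rates, and would differ for events that cluster early. The direction does not depend on the value chosen: at an unchanged hazard, later counts fall as patients leave. This affects how the safety results can be read. It does not affect the primary decision, the sample size or the interim boundaries.

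**What to change.** In 10.3.2, keep the crude table and state how timing will be summarised:

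- Report median and total time on drug.
- For Grade 3 or higher adverse events, drug-related SAEs and the 7.2.5 events of special interest, report first events per 100 patient-years with exact Poisson 90% limits.
- Count time at risk from first dose to the first event or 30 days after last dose, whichever comes first. For other malignancies, run it to the end of follow-up, because 7.2.5 collects them that far and a 30-day cut-off would drop late cases.
- Give each rate overall and for two broad periods, for example the first 12 months and later, with the number at risk at the start of each.

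The added sentence should name the window, because note 16 to the schedule in 5.0 describes adverse event tracking as running to the last study procedure, whereas 7.0 ends it 30 days after last use.

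The cost is one or two sentences and one table. Event onset dates are already needed for a timing summary, and dosing is tracked by study calendar and pill count (4.2). No visits, patients or type I error are spent. The limits will be wide at about 36 patients, as step 4 shows, so the table should be labelled descriptive.

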## STUDY SCHEMA

Patients must receive at least 4 cycles of induction chemotherapy with or without auto-SCT, including R-CHOP (with or without alternating R-DHAP), R-Hyper-CVAD, or R-bendamustine.

Per Cheson 2007 criteria.

During treatment, 1 cycle = 28 days. Patients will be evaluated (and drug will be dispensed) prior to each cycle for the first 6 months, then every 3 cycles thereafter for the remainder of treatment. See section 4.2 for the provision of 6-month visits after 2 years.

Follow-up schedule for patients off-treatment will be every 3 months up to 2 years post-first dose, then every 6 months up to 4 years post-first dose. Date of progression will be documented as well.

Study Numbers: NU 14H06  
PCI-32765MCL2003Initial version: September 24, 2014  
AMD 11: ver. date 08.06.2022**STUDY SUMMARY**

Title	A Phase II Clinical Trial Evaluating Ibrutinib Maintenance Following Intensive Induction for Patients with Previously Untreated Mantle Cell Lymphoma (MCL)
Version Date	August 8, 2022 (Amendment 11)
Phase/Design	Phase II, single-arm, multicenter, open-label study
Study Center(s)	Lead site: Northwestern University Participating sites: University of Michigan, University of Utah, and Dana Farber d/b/a Massachusetts General Hospital
Objectives	
Primary objective: Determine the 3-year PFS in patients with previously-untreated MCL who achieve response to intensive induction therapy and then receive maintenance Ibrutinib.
 
Secondary objectives:
 
 
• Toxicity
 
• Rates of conversion from PR to CR
 
• Median overall survival at 4 years
 
 
Exploratory objectives: Monitor MRD results by PCR and correlate with PFS and OS.

Sample Size	36 evaluable patients (patients who receive < 1 complete cycle of therapy will not be considered evaluable for efficacy endpoints and will be replaced; we estimate this to represent 3 or fewer subjects)

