### 3.0 SELECTION OF SUBJECTS

The target population for this phase II study is patients with histologically confirmed (previously untreated) mantle cell lymphoma (MCL) who have achieved response (CR or PR) to intensive induction systemic chemotherapy (with or without ASCT). This will be a multicenter trial conducted at Northwestern University. Northwestern University will serve as the lead site and coordinating center for this study. Participating sites will include University of Utah, and Dana Farber d/b/a Massachusetts General Hospital.

A total of 36 *evaluable* subjects will be needed for this trial (defined as having received  $\geq$  1 complete cycle of treatment). Approximately 5 potentially eligible patients are seen per month, and it is anticipated that at least 2 per month will be accrued *once the protocol is open and enrolling at all sites*. Potential patients may be referred to the Principal Investigator (PI) at Northwestern University or to the local PI at each participating site.

Eligibility will be evaluated by the study team according to the following criteria. Eligibility waivers are not permitted. Subjects must meet all of the inclusion and exclusion criteria to be registered to the study. Study treatment may not begin until a subject is registered. Please refer to Section 11.4 for complete instructions regarding registration procedures.

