## 6.0 ENDPOINT ASSESSMENT

### 6.1 Primary Endpoint

The primary endpoint will be progression-free survival (PFS) at 3 years. PFS will be measured from start of treatment to time of progression or death from any cause. Progression-free survival will be defined as the absence of either progression or death from any cause. Progression will be evaluated using Cheson 2007 criteria (Revised Response Criteria for Malignant Lymphoma, modified – please see Appendix II). Evidence of clinical progression will be documented by imaging (CT scan or MRI) for patients who have measurable disease. Any patient who receives at least one dose of study treatment will be evaluable for this endpoint.

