#### 6.2.2 Rate of conversion from PR to CR

Progression will be evaluated using Cheson 2007 criteria (Revised Response Criteria for Malignant Lymphoma, modified). Patients must have already achieved either PR or CR during induction chemotherapy prior to enrolling in this study. Patients with measurable disease at time of enrollment will have it followed with imaging. Only patients who had a PR at the time of registration and who complete  $\geq 1$  complete cycle of ibrutinib maintenance therapy will be evaluable for this endpoint. Please refer to appendices for a summary of Cheson criteria.

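### The PR-to-CR conversion rate leaves out PR patients who do not complete one cycle, which will usually leave the rate unchanged or raise it relative to all treated PR patients

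*Combined protocol and SAP*

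**What the plan says.** Two sections define the analysis set for the conversion rate in the same way. Section 6.2.2 reads "Only patients who had a PR at the time of registration and who complete" at least one full cycle are evaluable, and section 10.3.2 repeats this: "only patients who had a PR at the time of registration and who complete" at least one full cycle. On the estimate itself, section 10.3.2 says "These rates will be calculated as a proportion together with exact 90% confidence limits". No test or threshold is attached. Neither section says how a patient with no post-baseline response assessment is to be counted.

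Elsewhere the plan has two rules for efficacy evaluability:

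- Section 6.1, for PFS: "Any patient who receives at least one dose of study treatment will be evaluable for this endpoint".
- Study Summary, sample size entry: "patients who receive < 1 complete cycle of therapy will not be considered evaluable for efficacy endpoints and will be replaced". On how many: "we estimate this to represent 3 or fewer subjects".
- Section 3.0 ties the 36 evaluable subjects to at least one complete cycle: "subjects will be needed for this trial (defined as having received" that amount of treatment.
- Section 6.2.1 still speaks of replacement: "including those who are replaced for efficacy endpoints".
- Section 10.2 applies the 25/26 decision rule among the 36 evaluable patients.

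On assessment timing, footnote 7 to the section 5.0 schedule puts imaging at baseline and then after cycles 3 and 6. It allows an end-of-treatment scan, where clinically appropriate, for patients who stop early for a reason other than progression. Footnotes 13 and 14 put repeat marrow biopsy or endoscopy, where required, after 6 cycles.

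**The concern.** Completing a cycle is a post-baseline event. A PR patient who stops in the first 28 days because of toxicity, progression or death leaves the denominator, while a similar patient who stops a few weeks later stays in. The reported rate then describes PR patients who got through the first cycle, not PR patients who started ibrutinib, and the difference will tend to run in the favourable direction.

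The cut does not work as an assessability rule either. A patient who leaves in cycle 2 has had no scheduled scan, yet is kept. What separates the two patients is how early treatment ended, not whether response could be measured. The plan gives no reason for placing the threshold at one cycle.

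At stake is how a small descriptive proportion is read: a reader may take it as what a PR patient starting maintenance can expect.

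**Working it through.** **The plan's own figures.** The documents give no figure for this endpoint: no expected number of PR entrants and no expected conversion rate. The one stated design figure, 26 or more of 36 for the primary endpoint, does reproduce (exact binomial: type I error 0.0904 at 60%, power 0.9111 at 80%), but it does not bear on this point.

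**Inputs.**

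- From the documents: at most 3 patients expected with less than one cycle, PR and CR entrants combined (Study Summary); exact 90% limits (section 10.3.2).
- Assumed: n = 6 to 18 evaluable PR patients; conversion of roughly 33% to 50%; d = 0 to 3 excluded PR patients. The value d = 3 requires every early leaver to have been in PR.

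**Formula.** With x conversions among n evaluable PR patients, the planned rate is x/n. If the d excluded patients are added as not converted, the rate is x/(n+d). The shift is

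x/n − x/(n+d) = xd / [n(n+d)],

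which is zero when d = 0 and otherwise cannot be negative.

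**Results** (Clopper-Pearson 90% limits for the planned rate):

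| Planned rate | Exact 90% limits | d = 1 | d = 2 | d = 3 |
|---|---|---|---|---|
| 4/12 = 33.3% | 12.3% to 60.9% | 4/13 = 30.8% | 4/14 = 28.6% | 4/15 = 26.7% |
| 6/12 = 50.0% | 24.5% to 75.5% | 6/13 = 46.2% | 6/14 = 42.9% | 6/15 = 40.0% |
| 9/18 = 50.0% | 29.1% to 70.9% | 9/19 = 47.4% | 9/20 = 45.0% | 9/21 = 42.9% |
| 3/6 = 50.0% | 15.3% to 84.7% | 3/7 = 42.9% | 3/8 = 37.5% | 3/9 = 33.3% |

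For 4/12 with d = 1 the shift is 4 × 1 / (12 × 13) = 2.6 points. For 3/6 with d = 3 it is 3 × 3 / (6 × 9) = 16.7 points, the largest in the assumed range. With d = 1 the shift lies between about 2 points (6/18 to 6/19) and 7 points (3/6 to 3/7).

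**Does the direction always hold?** Only if excluded patients count as not converted. If c of the d excluded patients had a documented CR, the all-treated rate is (x+c)/(n+d), which exceeds x/n whenever c/d is greater than x/n. One excluded patient with a CR on an optional end-of-treatment scan would turn 6/12 = 50.0% into 7/13 = 53.8%. That is possible under footnote 7, but no scheduled assessment leads to it.

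**The case against.** The best defence is that the plan states its population openly, twice and identically, and the rate is a valid estimate for that population. It overstates only if it is read as applying to every PR patient who starts ibrutinib. The endpoint is secondary and descriptive, the shift is zero if no early leaver was in PR, and every shift shown lies inside a wide exact interval. All of this stands, and it limits the weight of the point. It does not remove it: the interval describes sampling error and does not correct for a selected denominator, and the one-cycle cut is not explained by assessability.

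Two stronger readings are tempting, and the documents do not support either.

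- **That everyone excluded is a proven non-converter, so the rate is necessarily too high.** With first imaging after cycle 3, a cycle-1 leaver is normally unassessed rather than shown not to have converted, and the optional end-of-treatment scan could record a CR. Counting unassessed patients as not converted is a common convention, but it is an imputation.
- **That the rule breaks an intention-to-treat principle governing the primary endpoint.** That phrase appears only in the Appendix IV change log, as the reason for the Amendment 4 edit to section 6.1. In the current text the Study Summary, section 3.0 and section 6.2.1 keep a one-cycle evaluable set with replacement, and section 10.2 counts among those evaluable patients. The conversion rule agrees with that set and differs only from section 6.1. The primary analysis set is itself unreconciled, which is a wider matter than this endpoint.

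**Conclusion.** The point holds as a modest one. Sections 6.2.2 and 10.3.2 condition the conversion rate on completing a cycle, and this will usually leave the rate unchanged or raise it relative to all treated PR patients.

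Under the assumed values the difference is nil if no early leaver was in PR, about 2 to 7 points with one, and at most about 17 points, which needs only 6 evaluable PR patients and all three early leavers in PR. These sizes rest on assumed PR counts and conversion rates, on the plan's estimate of 3 or fewer early leavers, and on counting unassessed patients as not converted. No hypothesis test or trial decision is affected, so this is a cheap improvement and not a flaw in the design.

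**What to change.** In sections 6.2.2 and 10.3.2:

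- Define the denominator as all patients in PR at registration who received at least one dose.
- Count a documented CR on any post-baseline assessment, scheduled or not, as a conversion.
- Count patients with no post-baseline assessment as not converted, and report how many there are.
- Report the one-cycle subset as a sensitivity analysis, with the same exact 90% limits.

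The Study Summary sentence that makes patients with less than one cycle not evaluable for efficacy endpoints must change in the same amendment, or the new wording will contradict it. The same edit should reconcile the Study Summary, section 3.0, section 6.1, section 6.2.1 and section 10.2 on who is evaluable for efficacy and who is replaced.

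The cost is wording only: no new patients, visits or data. The reported conversion rate becomes slightly less favourable, and part of that drop comes from the convention for unassessed patients; showing both rates lets a reader see how much.

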#### 2.2.3 Determine median overall survival (OS) after 4 years.

Patients will be evaluated monthly for the first 6 months on treatment, then every 3 months thereafter. Patients who go off treatment will continue to be followed for survival up to a maximum of 4 years post-first dose. Follow-up will occur every 3 months (up to 2 years after the first dose of treatment) and then every 6 months thereafter (up to 4 years post-first dose). Median OS after 4 years will be calculated.

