#### **4.7 Duration of Follow Up**

Patients who complete 4 years of maintenance therapy with ibrutinib will have one final follow-up study visit approximately 30 days post-last dose. Patients who discontinue study therapy prior to this point will be followed up to a maximum of 4 years (post-first dose of treatment) for survival endpoints (including date of progression). Follow-up will occur every 3 months (up to 2 years after the first dose of treatment) and then every 6 months thereafter (up to 4 years post-first dose).

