#### 6.2.3 Median overall survival at 4 years

Overall survival (OS) will be defined as the duration of time from start of treatment up to 4 years from the start of study treatment.

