### **10.1.2 Secondary Endpoints**

Adverse events will be defined according to the National Cancer Institute's Common Terminology Criteria for Adverse Events (NCI CTCAE) version 4.03. The occurrence and severity of each will be recorded. The rate of conversion from PR to CR will be calculated. Overall survival (OS) will be assessed after 4 years.

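### Section 10.3.2 asks for a five-year overall survival estimate although survival follow-up ends at about 4 years, and footnote 11 of the Schedule of Events conflicts with the rest of the protocol on follow-up after progression

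*Combined protocol and SAP*

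**What the plan says.** **Time point.** The OS paragraph of section 10.3.2 opens with the aim "To determine median overall survival (OS) after 4 years". It then specifies Kaplan-Meier curves and states that "the five-year point on this curve, along with 90% confidence limits, will be determined". Two sentences later it says that patients off treatment are "followed for survival up to a maximum of 4 years post-first dose".

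The other OS statements all use 4 years:

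- Study Summary: "Median overall survival at 4 years".
- Section 2.2.3: "Median OS after 4 years will be calculated".
- Section 6.2.3 defines OS as "the duration of time from start of treatment up to 4 years from the start of study treatment".
- Section 10.1.2: "Overall survival (OS) will be assessed after 4 years".
- Section 4.7 follows early discontinuers to 4 years from first dose. Patients who finish 4 years of treatment "will have one final follow-up study visit approximately 30 days post-last dose".

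**Follow-up after progression.** Footnote 11 of the Schedule of Events (section 5.0) first says that patients who stop treatment early are followed for survival endpoints for up to 4 years from first dose. Its next sentence makes the 3-monthly and 6-monthly follow-up run only until progression. Section 4.8 says that at disease progression treatment ends and follow-up goes on. Section 7.2.5 refers to survival follow-up after progression when it sets the reporting period for new malignancies. Note 4 of the Study Schema gives the off-treatment schedule to 4 years and adds only that the progression date is recorded. Sections 2.2.3, 4.7 and 10.3.2 contain no stop at progression.

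**The concern.** The five-year point is the only OS time point that the analysis section names, and it lies beyond the survival data that the protocol collects. An analyst would have to depart from the text, or carry the last value of the curve forward and label it five-year survival. The other named summary, the median, may not be reached within 4 years.

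Footnote 11 matters more, because it governs data collection. Patients who progress are at higher risk of death than those who do not. If survival contact stops at progression, OS is censored for a reason linked to prognosis, and Kaplan-Meier then overstates survival. Analysis cannot recover deaths that were never collected. The exploratory regression of OS on minimal residual disease (section 10.3.3) uses the same data.

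**Working it through.** **1. The primary design, to see whether it is touched.** Section 10.2 gives 36 patients, success at 26 or more, and 60% against 80%. Exact binomial: P(X ≥ 26 | n = 36, p = 0.60) = 0.0904 and P(X ≥ 26 | n = 36, p = 0.80) = 0.9111. The stated 10% type I error and 90% power reproduce. Neither depends on OS.

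**2. End of survival follow-up against the requested time point.** Inputs: 4 years from first dose (4.7, 6.2.3, 10.3.2), plus about 30 days for completers (4.7).

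- Early discontinuers: 4.00 years.
- Completers: (4 × 365.25 + 30) / 365.25 = 1491 / 365.25 = 4.082 years.
- Shortfall for completers: 5 − 4.082 = 0.918 years, or 0.918 × 12 = 11.0 months.
- Planned number under survival follow-up at five years: 0 of 36. The curve would be defined there only in the trivial case that it had already fallen to zero.

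**3. Later contacts that are not survival follow-up.** Footnote 15 rechecks certain hepatitis B carriers until 6 months after stopping ibrutinib, which is about 4.5 years for a completer. Sections 7.0, 7.1 and 7.3.3.3 follow some adverse events to resolution without a fixed end. These contacts reach only patients selected by carrier status or by an event, and 6.2.3 caps OS at 4 years in any case.

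**4. Is the median a safe fallback?** OS cannot be below PFS. Assume a constant hazard (not in the documents), so that 4-year PFS = (3-year PFS)^(4/3).

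- 3-year PFS 60%: 0.60^(4/3) = 50.6%.
- 3-year PFS 80%: 0.80^(4/3) = 74.3%.

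On that assumption true 4-year OS is at least 50.6% even at the null, so the median may well not be reached. The 4-year rate is the more dependable summary.

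**5. Ceiling on the footnote 11 bias.** Assume 36 patients and no other loss before 4 years. With all D deaths recorded, 4-year OS is 1 − D/36. If k deaths are lost through censoring at progression, each of the D − k recorded deaths still lowers the curve by at least 1/36, because Kaplan-Meier passes a censored patient's weight to later times. The estimate is then at most 1 − (D − k)/36, and the upward shift is at most k/36.

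| Missed deaths k | Maximum shift (percentage points) |
|---|---|
| 1 | 2.8 |
| 3 | 8.3 |
| 5 | 13.9 |

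**6. How many patients the footnote could touch.** Keep the constant hazard and assume that 10% to 20% of PFS events are deaths without progression (not in the documents). Expected progressions by 4 years = 36 × (1 − d) × (1 − 4-year PFS).

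- 3-year PFS 80%, d = 0.2: 36 × 0.8 × 0.257 = 7.4.
- 3-year PFS 60%, d = 0.1: 36 × 0.9 × 0.494 = 16.0.

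This is the pool of patients, not the number whose follow-up stopped or whose death was missed.

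**The case against.** **The five-year wording is a slip with a recoverable meaning.** The same paragraph opens with 4 years, and every other OS statement agrees. This largely stands: no data are lost, and by itself the error is small. It is still an operative instruction that cannot be carried out, and no other OS time point is given in that section.

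**Later contacts exist.** A reader might infer that nobody has any protocol contact after 4.08 years. The documents do not support that, given the hepatitis B rechecks and the open-ended adverse event follow-up. The point holds for survival follow-up only.

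**Footnote 11 is outnumbered.** The intention to follow past progression is clear from the other sections, although 7.2.5 presupposes such follow-up rather than establishing it. This stands as evidence of intent. But the footnote belongs to the table that sites work from, and it ties the whole 3- and 6-monthly schedule to progression, so a site could reasonably stop there.

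**Some deaths would be caught anyway.** Section 7.2.3 requires all serious adverse events, including deaths, to be reported through 30 days after the last dose whatever their cause. Section 7.3.2 extends reporting beyond 30 days for events attributed to the drug. This stands: the exposure is limited to deaths outside those rules.

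**The ceiling is not an estimate.** A reader might set k/36 beside the width of the OS confidence interval and conclude that a handful of missed deaths would move the estimate by that much. That comparison holds only at the maximum, and the documents give neither the number of missed deaths nor the OS to be expected.

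**Visit windows.** A reader might also ask for a closing check because the last visit may fall 10 days early. The window is symmetric and completers have a later visit, so this is a preference rather than a defect.

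**Conclusion.** The plan is wrong as written in two places, and both should be corrected. The five-year OS estimate is not obtainable: survival follow-up ends at 4.00 to 4.08 years and the endpoint itself is capped at 4 years. That conclusion needs no assumption beyond the stated follow-up. Kaplan-Meier OS to 4 years remains available.

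Footnote 11 contradicts its own preceding sentence, note 4 of the Study Schema, and sections 4.8 and 7.2.5. Its effect depends on conduct. If it was applied, OS would be informatively censored and biased upward, by at most 2.8 percentage points per missed death with 36 patients and no other loss. A reader might infer that the OS results are in fact biased. The documents do not show that any site stopped at progression, and they do not give the size of any bias.

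OS is a descriptive secondary endpoint without a hypothesis test. The primary decision rule and its error rates are unaffected.

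**What to change.** 1. In section 10.3.2, replace the five-year point with the 4-year Kaplan-Meier OS rate and its 90% limits. Report the median only if it is reached.
2. Reconcile footnote 11 with sections 4.8 and 7.2.5 so that vital status is collected to 4 years from first dose regardless of progression, unless consent is withdrawn.
3. Identify any patient whose follow-up stopped at progression, retrieve vital status, and report how many there were.

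Naming death from any cause as the event and stating the censoring rule in section 6.2.3 would be useful tidying, but is optional.

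The cost is small: amendment wording and a one-time retrieval. The retrieval is confined to patients who progressed, expected to be about 7 to 16 of 36 under the assumptions in the working, and within them to those whose follow-up actually stopped. The documents do not give that number. Sample size is unchanged.
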